### 1.2 Specific Aim 2. Secondary Outcomes--Stroke Education and Prevention:

Many patients with stroke know little about the causes of their condition and consequently have poor control of stroke-related risk factors. Improving patient knowledge about stroke can therefore help to prevent stroke recurrence and to optimize patient outcomes. While all certified stroke centers include patient education as a priority during the acute stroke admission, patients and their families may not be in the best position to benefit from such education at this time as compared to once they have returned to their home. Aim 2 will compare two different approaches to patient education in their impact on stroke knowledge, hypothesizing that both are effective, and are effective to an equal extent. As an extension of this issue, the degree of gains in stroke knowledge is hypothesized to be related to the extent to which patients implement appropriate lifestyle changes.

**1.2.1** Subjects, having received targeted educational material for 6 weeks, will significantly increase knowledge related to stroke prevention and stroke risk factor control, measured as the change in percentage of questions answered correctly on the Stroke Education Exam from Screening Visit to Post-Therapy Visit.

**1.2.2** The change in percentage of questions answered correctly on the Stroke Education Exam from Screening Visit to Post-Therapy Visit among subjects using the telerehabilitation system will be comparable to the change in percentage of questions answered correctly on the Stroke Education Exam among subjects using a traditional paper booklet-based method.

**B.1.3** Increased stroke knowledge will be positively correlated with improvement in weight and blood pressure control.

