### 5.3.2 Baseline Visit

The Baseline Visit occurs 1-21 days after the screening visit (target value = 7 days), and 4-36 weeks after stroke onset. The study site will call the subject 1-2 days before this visit, reminding him/her of the time and place of the visit. The initial portion of this visit is performed by the Assessment Therapist. The Fugl-Meyer test will be rescored, after which subjects will be scored on the Handedness Inventory, and the Stroke Impact Scale-Hand Domain. The amount of any therapy (OT, PT, SLT) that the subject received since the Screening Visit and any new medications will be documented. Each subject will be asked to sign a behavioral contract.

After final eligibility is determined, the remainder of this visit will be performed by one of the site's certified Treatment Therapist. Subjects will be randomized via WebDCU™ to 6 weeks of (a) in-clinic therapy or (b) home-based telerehabilitation in a 1:1 ratio. The Treatment Therapist will provide the subject with the PACES Scale and OPS. The Treatment Therapist will then explain the details related to the subject's newly assigned rehabilitation therapy. For

subjects randomized to in-clinic therapy, this will include review of the content and design of therapy as well as details regarding the location where therapy will be delivered. For subjects randomized to telerehabilitation, the Treatment Therapist will review of the content of therapy and provide training on use of the telerehabilitation system.

The Treatment Therapist and the subject will then schedule the six weeks of therapy sessions.

Note that the Baseline Visit may be broken up into two separate visits not more than 3 days apart at the judgment of the research team. This is not encouraged but it is recognized that this may be useful for selected patients. If this Visit is broken into two separate visits, this will not change the fact that the first therapy session must be 1-10 days post-randomization.

### 5.3.3 Therapy Weeks 1- 6

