## 8. STATISTICAL CONSIDERATIONS, DATA ANALYSIS AND DATA MONITORING

In the study, populations used for testing comparable efficacy, the non-inferiority margin proposed for determining comparable efficacy, the statistical procedures used for summarizing and testing the primary and secondary comparable efficacy endpoints, and sample size justification for the proposed study. All analyses are two-tailed and use  $\alpha=0.05$ .

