**Determination of sample size:**

The objective of this study is to assess comparable efficacy of telerehabilitation vs. in-clinic intensive arm motor rehabilitation therapy with respect to the mean  $\Delta_{FM}$  from the Baseline Visit to the 30 Day Follow Up Visit, using a non-inferiority margin of 2.05. Based on our pilot study, the mean  $\Delta_{FM}$  in the telerehabilitation group is expected to be 4.80 with SD=3.80; extension to multiple sites and enrollment of subjects at earlier time points post-stroke may be associated with larger variance, and so a SD=4.0 is assumed. Comparable efficacy will be established provided that the lower bound of the 95% confidence interval for the difference in the  $\Delta_{FM}$  between treatment groups is greater than -2.05. Assuming 80% power, the study will therefore seek to attain 30 Day Follow Up data on N=124 subjects (62 per arm). If the dropout rate is as high as 20%, then as many as 155 subjects may need to be enrolled.

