**8.5 Secondary outcome measures:****Stroke education**

- Gains in stroke knowledge from Screening Visit to Post-Therapy Visit, measured as the change in percentage of questions answered correctly on the Stroke Education Exam

In order to determine whether targeted educational material significantly increases subject knowledge related to stroke, the Stroke Knowledge Exam will be administered twice, once at the Screening Visit then again at the Post-Therapy Visit. A repeated measures ANOVA will be performed to determine if the percentage of Stroke Knowledge Exam answered correctly increases significantly from the Screening Visit to the Post Therapy Visit, controlling for days from stroke onset to randomization, initial Stroke Knowledge Exam score (at the Screening Visit), age, and enrollment site. To determine if gains in stroke knowledge vary according to the method by which stroke education is delivered, analysis will be repeated adding a time X group interaction term. Weight and blood pressure will be measured during the Screening Visit as well as during the Post Therapy Visit. In order to determine whether gains in stroke knowledge are associated with improvements in stroke risk factor control, the relationship between gains in stroke knowledge (the change in percentage of questions answered correctly on the Stroke Education Exam from the Screening Visit to the Post Therapy Visit) and improvement in weight and blood pressure control (change in weight, change in systolic blood pressure, and change in diastolic blood pressure) will be examined, controlling for days from stroke onset to randomization, Stroke Knowledge Exam score at Screening Visit, age, and enrollment site, and using a Bonferroni-adjusted alpha = 0.017; again, analyses will be repeated by adding a time X group interaction term.

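### The Stroke Knowledge analysis uses the Screening score as both a response and a covariate, so with main-effect covariates the stated baseline adjustment is empty and the arm comparison loses precision

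*Combined protocol and SAP*

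**What the plan says.** Section 8.5 (Stroke education) states that "the Stroke Knowledge Exam will be administered twice, once at the Screening Visit then again at the Post-Therapy Visit". The first analysis is described thus: "A repeated measures ANOVA will be performed to determine if the percentage of Stroke Knowledge Exam answered correctly increases significantly from the Screening Visit". Its second time point is Post-Therapy. The adjustment is worded separately: "controlling for days from stroke onset to randomization, initial Stroke Knowledge Exam score (at the Screening Visit), age, and enrollment site". For the comparison of the two education methods, "analysis will be repeated adding a time X group interaction term". No other interaction is named for this analysis, and no covariance structure or estimation method is given.

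The model serves two objectives in section 1.2: the knowledge gain (1.2.1) and the comparability of the gain between arms (1.2.2). The aim is introduced as "hypothesizing that both are effective, and are effective to an equal extent". No margin is given for the comparison.

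Elsewhere the plan handles a starting score differently. The primary Fugl-Meyer analysis (section 8.3, primary efficacy analysis) and the PACES analysis (section 8.5) are both ANCOVAs on change with the baseline value as a covariate, so there the baseline value is not also a separate response.

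**The concern.** The Screening score appears on both sides of the model. At the first visit the outcome is regressed on itself; at the second it is regressed on its own starting value; one coefficient has to serve both. A reader of the plan would take the arm comparison to be adjusted for initial knowledge, and as written it is not.

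This matters mainly for 1.2.2. The covariate-adaptive randomization in section 5.2 balances days post-stroke, Fugl-Meyer score and site, but not initial knowledge. A real adjustment would therefore correct chance imbalance in the exam score and narrow the interval for the arm difference. Where the hoped-for result is that the arms are alike, a wider interval than necessary is a direct cost. The double use also makes the standard error depend on how the model is fitted, which the plan leaves open.

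**Working it through.** The plan states no sample size, power or standard error for this analysis, so there is no figure to reproduce. The check is algebra, supported by fitted examples and simulation.

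**Inputs.** Two responses per subject and the covariate list come from section 8.5. Two-sided alpha of 0.05 comes from section 8. The numbers, 124 subjects at 62 per arm, come from the sample size section, where they refer to 30 Day data; using them for the Post-Therapy exam is an assumption. Also assumed: complete data at both visits, equal SDs at both visits (set to 1), and a Screening-to-Post correlation ρ of 0.3, 0.5 or 0.7. ρ is not in the documents.

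**1. The adjustment cancels.** With main-effect covariates, subject i has expected scores
- Screening: a + γ·g + β·y0
- Post-Therapy: a + τ + (γ + δ)·g + β·y0

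The difference is τ + δ·g. β drops out, so the time effect τ and the time by group effect δ are estimated from raw change. The same holds for days from onset, age and site. In fitted examples the time by group estimate was identical with and without the Screening score: −0.1359, −0.1735 and −0.1132 at ρ = 0.3, 0.5 and 0.7.

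**2. Precision given up.** Per-subject variance is 2(1−ρ) for raw change and 1−ρ² for ANCOVA. The ratio is (1−ρ²)/[2(1−ρ)] = (1+ρ)/2. The standard error of the arm difference is the square root of (variance × 2/62).

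| ρ | Variance ratio | Reduction | SE, raw change | SE, ANCOVA |
|---|---|---|---|---|
| 0.3 | 0.65 | 35% | √(1.40×2/62) = 0.213 | √(0.91×2/62) = 0.171 |
| 0.5 | 0.75 | 25% | √(1.00×2/62) = 0.180 | √(0.75×2/62) = 0.156 |
| 0.7 | 0.85 | 15% | √(0.60×2/62) = 0.139 | √(0.51×2/62) = 0.128 |

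Simulation (4,000 trials per ρ, no true effect) gave empirical SDs of 0.213, 0.181 and 0.140 for raw change and 0.170, 0.157 and 0.129 for ANCOVA. ANCOVA type I error was 4.5%, 5.2% and 5.3%.

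**3. The standard error depends on the fit.**

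*Classical split-plot ANOVA.* The within-subject error term is untouched by a main-effect covariate, so with two visits the time by group test is a t-test on change. Simulated type I error was 5.0%, 5.0% and 5.1%.

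*Random intercept or pooled error.* The common coefficient on the Screening score is the average of 1 and ρ, that is (1+ρ)/2. The between-visit residual covariance is then −(1−ρ)²/4, which is negative. A random intercept cannot represent that, so its variance goes to about zero. The model variance of the change becomes (1−ρ)²/2 + (1−ρ²) against a true 2(1−ρ), a ratio of (3+ρ)/4.

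| ρ | SE ratio √[(3+ρ)/4] | Type I error, 2[1−Φ(1.96 × ratio)] | Simulated |
|---|---|---|---|
| 0.3 | 0.908 | 7.5% | 7.4% |
| 0.5 | 0.935 | 6.7% | 7.0% |
| 0.7 | 0.962 | 5.9% | 6.2% |

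*Unstructured covariance.* The model is degenerate. As the Screening coefficient approaches 1, the Screening residual variance goes to zero and the likelihood grows without bound (log-likelihood at ρ = 0.5: 101 at a coefficient of 0.5, 586 at 0.99, 1157 at 0.9999).

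**4. The overall gain.** Section 3 reports a pilot rise from 22.8 to 31.7 out of 40 in 12 subjects, p=0.0007. That is 8.9/40 = 22.25 percentage points. If the p-value is from a paired t-test (t about 4.65 on 11 df), the SD of change is about 16.6 points. With 124 subjects the SE would be 16.6/√124 = 1.49, and 22.25/1.49 is about 15. An SE 9% too small does not alter that conclusion.

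**The case against.** Three points can be made for the plan.

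First, it names a repeated measures ANOVA, not a mixed model, and the classical version has a valid standard error. This stands. A reader might infer that the analysis as written inflates type I error; the documents do not support that. Inflation needs a random-intercept or pooled-error fit, which the text neither specifies nor rules out. Where it occurred, it would produce too many false differences between arms. That works against the hypothesis of equal gains and would not create a false claim of comparability.

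Second, the outcome in section 1.2 is a change, and the next analysis in section 8.5 adjusts the gain for its starting score, so the authors may have meant each covariate to be crossed with time. Under that reading the time by group test is the ANCOVA on change, and it is valid. But the text names only one interaction. With crossing, the time effect is also read at covariate zero (age zero, exam score zero) unless covariates are centred, and the plan mentions no centring. This reading shows ambiguity; it does not repair the text.

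Third, the stakes are modest: a secondary, non-motor outcome, and raw change is unbiased under randomization. This too stands. A reader might also extend the point to all of Aim 2, but the risk-factor association (B.1.3) is a separate model without the double use. Nor does every other endpoint already use the proposed form: the compliance and OPS models have no change score and no starting value of the outcome.

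**Conclusion.** The concern holds in a limited form. The Screening score is used twice. With covariates as main effects and complete two-visit data, the stated baseline control has no effect on the time or time by group estimate. The comparison for 1.2.2 is then the unadjusted difference in change, and ANCOVA would lower its variance by (1−ρ)/2: about 35%, 25% or 15% at assumed correlations of 0.3, 0.5 or 0.7. This does not depend on the SD, but it assumes equal SDs at the two visits.

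The standard-error problem is conditional: none in a split-plot ANOVA, and 4% to 9% too small with a random intercept or pooled error over the same range of correlations. The conclusion on 1.2.1 is unlikely to change, and the primary endpoint is not touched. This is an improvement available at almost no cost, not a flaw that threatens the trial's main result.

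**What to change.** In section 8.5 (Stroke education):

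- For 1.2.2, replace the repeated measures model with an ANCOVA of change in percent correct on treatment group, with Screening exam score, days from stroke onset to randomization, age and enrollment site as covariates. Report the adjusted difference with its 95% CI.
- For 1.2.1, report the mean change and 95% CI from the same model with covariates centred and the two arms averaged, or use a paired test.
- State that the Screening score is not a covariate in any model in which it is also a response.

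The cost is SAP wording. No visit, measurement or sample size changes, and the form is the one the plan already uses for Fugl-Meyer and PACES.

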**Stroke patients lack key knowledge and this affects their outcomes.**

Compounding these issues is the overall modest control of stroke risk factors among survivors of stroke. At a time when patients are trying to recover and maintain function, many fail to control stroke risk factors. Risk factor control can prevent further vascular injury, recurrent stroke, myocardial infarction and progression of peripheral vascular disease—conditions that can have a large bearing on outcome after stroke. For example, the NHANES III study found that in 1,252 U.S. survivors of MI or stroke, blood pressure was controlled in only 53%; blood sugar, in only 50%; and blood cholesterol, in only 46%. While these results may be due to multiple factors, a likely contributor is that patients with stroke have limited knowledge about their condition. For example, 39% of ER patients with possible stroke could not name 1 sign or symptom of stroke in one study, and 40% of patients with stroke could not identify even a single stroke risk factor. Limited financial resources, time, and distance limit participation in educational programs in patients with neurological disease. Yet this issue is of particular importance after stroke, as 1 in 6 stroke survivors will have a recurrent stroke, which often introduces further disability. Education that improves awareness of control of modifiable stroke risk factors can improve risk factor control in patients with stroke. Attention to stroke education can maximize behavioral gains from a stroke telehealth system. Education of patients with stroke helps improve function and risk factor control, and thereby promotes favorable outcomes, and so is also a key focus in the current study

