### 8.1 Analysis of populations:

Primary efficacy analyses will be conducted on the Intent-To-Treat (ITT) Population, defined as all subjects who are randomized. Sensitivity analyses for efficacy will also be conducted on the Per-Protocol Population, defined as all subjects who complete assigned activities for at least 40 minutes at 15 or more of the 18 supervised therapy sessions over a period of time extending no more than 8 weeks. In ITT analysis, for missing data such as due to subject lost to follow-up, multiple imputation using all available evaluation data will be utilized. No interim analysis is planned.

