**Compliance and motivation.**

- Compliance with therapy, defined as the percentage of the 36 therapy sessions for which the subject completed assigned activities for at least 40 minutes

Compliance with rehabilitation therapy will be examined across all 36 sessions. For supervised sessions, a subject will be considered compliant if at least 40 min of assigned

therapy has been completed, determined from the therapist notes for subjects in the in-clinic group and from telerehabilitation system usage data for subjects in the telerehabilitation group. For unsupervised sessions, a subject will be considered compliant if at least 40 min of assigned therapy has been completed based on self-report for the in-clinic group and by telerehabilitation system usage data for subjects in the telerehabilitation group. To determine whether compliance with therapy differs according to treatment group, ANCOVA modeling will be used to examine compliance across the 36 sessions as a function of treatment group, controlling for days from stroke onset to randomization, age, and enrollment site. Secondary analysis will examine compliance with only the supervised therapy sessions, as well as compliance with only the unsupervised sessions.

**Motivation** (assessed along two independent dimensions):

- Activity-inherent motivation, defined as the change in score on the Physical Activity Enjoyment (PACES) Scale from baseline to end of the first week of therapy
- Consequence-related motivation, defined as the score on the Optimization in Primary and Secondary Control (OPS) Scale at the Baseline Visit

Activity-inherent motivation reflects how much a subject likes or dislikes an activity itself, independent of his or her commitment to the treatment goals. To measure this, the PACES Scale will be scored three times (at the Baseline Visit, after 3 supervised sessions, and after 18 supervised sessions). Activity-inherent motivation will be defined as the change in PACES score. Primary analysis will examine the change from baseline to end of week 1, while secondary analysis will examine change from baseline to end of week 6. To determine whether activity-inherent motivation is different for in-clinic vs. telerehabilitation therapy, ANCOVA modeling will examine differential change in PACES score between the two treatment groups, controlling for days from stroke onset to randomization, PACES score at the Baseline Visit, age, and enrollment site.

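### The models linking knowledge gain to change in weight and blood pressure leave out the Screening value of the outcome, which costs precision and can let regression to the mean mimic an association

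*Combined protocol and SAP*

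**What the plan says.** Section 1.2, objective B.1.3, states the hypothesis: "Increased stroke knowledge will be positively correlated with improvement in weight and blood pressure control".

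Section 8.5 (Stroke education) makes it operational as "improvement in weight and blood pressure control (change in weight, change in systolic blood pressure, and change in diastolic blood pressure"). The models are fitted "controlling for days from stroke onset to randomization, Stroke Knowledge Exam score at Screening Visit, age, and enrollment site", "using a Bonferroni-adjusted alpha = 0.017", and are then repeated with an interaction term for group. No subset of subjects is named. Section 8.1 defines the intent-to-treat population as "defined as all subjects who are randomized", though it does so for the primary efficacy analyses. The eligibility criteria in 13.2 contain no blood pressure or weight requirement. The natural reading is that everyone with data is analysed.

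Elsewhere the plan does adjust a change score for its own starting value. The primary ANCOVA in section 8 includes Baseline Fugl-Meyer. The PACES change model in 8.5 is fitted "controlling for days from stroke onset to randomization, PACES score at the Baseline Visit, age, and enrollment site". The knowledge model in 8.5 includes the Screening exam score.

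**The concern.** The covariate list for B.1.3 is the same as the one for the knowledge model earlier in 8.5. There, the Screening exam score is the starting value of the outcome. In B.1.3 it is the starting value of the predictor, and the starting value of the outcome is absent.

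Blood pressure varies from visit to visit, so a high Screening reading tends to be followed by a lower one whatever the subject has learned. Two things follow. Variation in change that the Screening value would explain stays in the residual and widens the interval for the slope. And if subjects with higher Screening pressure also gain more knowledge, their expected fall is credited to the knowledge gain. The plan gives no reason for treating these three outcomes differently from Fugl-Meyer and PACES.

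**Working it through.** **The plan's own figure.** Section 8 says "All analyses are two-tailed and use" an alpha of 0.05. With three outcomes, 0.05/3 = 0.0167, which rounds to the stated 0.017 (3 × 0.017 = 0.051). The alpha is reproduced.

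**Inputs.** From the plan: N = 124 with follow-up data (section 8, sample size), alpha 0.017 two-sided, and the covariates quoted above. Assumed, because the documents do not give them: rho, the correlation of a measure between its two visits; equal variance at both visits; and c, the correlation of knowledge gain with the Screening value. The other covariates are left out of the calculation, so rho and c are to be read as what remains after adjusting for them.

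**Step 1, precision.** With variance s² at each visit:
- variance of raw change = 2s²(1 − rho)
- variance after adjusting for the Screening value = s²(1 − rho²)
- ratio = 2/(1 + rho)

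| rho | ratio | adjusted N of equal precision, 124 × (1+rho)/2 |
|---|---|---|
| 0.4 | 1.43 | 87 |
| 0.5 | 1.33 | 93 |
| 0.7 | 1.18 | 105 |
| 0.8 | 1.11 | 112 |

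At rho of 0.4 to 0.7, the planned analysis of 124 subjects is about as precise as an adjusted analysis of 87 to 105. The ratio tends to 1 as rho tends to 1, so the loss for weight is small if weight is very stable between visits.

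**Step 2, false association.** Change and Screening value have correlation −√((1 − rho)/2): −0.50 at rho 0.5 and −0.39 at rho 0.7. With no true effect of knowledge, the unadjusted correlation of gain with change is c times this. For c = 0.2 and rho = 0.5 it is −0.10. Fisher's z gives atanh(0.10) × √121 = 1.10 against a critical value of 2.387, so rejection is about 10%. Simulation (2,000 runs per setting, N = 124) gives:

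| c | unadjusted, rho 0.5 | unadjusted, rho 0.7 | adjusted, rho 0.5 / 0.7 |
|---|---|---|---|
| 0 | 2.0% | 1.5% | 1.6% / 1.9% |
| 0.1 | 3.4% | 2.5% | 1.8% / 1.5% |
| 0.2 | 10.1% | 7.3% | 1.4% / 1.5% |
| 0.3 | 25.3% | 12.9% | 2.1% / 1.5% |

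The nominal rate is 1.7%. The adjusted test stays there within simulation error; the unadjusted test does so only at c = 0. A positive c produces falls that go with knowledge gain, which is the direction the aim predicts.

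**Step 3, would a restricted analysis be better?** Take the background figure in section 2.1, where "blood pressure was controlled in only 53" per cent of survivors of MI or stroke, as a guess for this sample. Then 47% of 124, about 58, are uncontrolled. Power = Φ(atanh(r)√(N − 3) − 2.387), with the pooled r taken as the weighted mean of the two groups:

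| true r, uncontrolled / controlled | pooled r | power, all 124 | power, 58 uncontrolled |
|---|---|---|---|
| 0.3 / 0 | 0.141 | 0.20 | 0.46 |
| 0.3 / 0.15 | 0.2205 | 0.53 | 0.46 |
| 0.3 / 0.3 | 0.30 | 0.85 | 0.46 |

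Power is equal at a pooled r of 0.206, which needs r = (0.206 − 0.141)/0.53 = 0.12 in controlled subjects, about 0.4 of the value in the uncontrolled. Restriction gains power only below that.

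**The case against.** The best defence is that the omission need not bias anything. The models regress change on knowledge gain, not on treatment or on the Screening value. Regression to the mean distorts that slope only if knowledge gain is correlated with the Screening value after the listed covariates, and the documents give no such correlation. One obvious route, in which poorly informed subjects have both higher pressure and more to learn, is largely blocked because the Screening exam score is already in the model. This stands: the false-positive rates are conditional on an assumption, and at c = 0 the test keeps its level. It does not answer the loss of precision, and it gives no reason to leave out a covariate that is already collected.

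A reader might go further and infer that the analysis cannot measure improved control at all, because a fall in a subject already at target counts the same as a fall in one above target, and that the above-target subset should therefore be the main analysis. The documents do not support this:
- Section 8.5 states its definition of improvement in control, and it is continuous change.
- Controlled subjects can lose control, so a link with knowledge can show in them as pressure or weight held steady.
- Section 1.2 ties the hypothesis to appropriate lifestyle changes in patients generally, not only in the uncontrolled.
- The 53% comes from a mixed survey of MI and stroke survivors and covers blood pressure only; nothing in the documents gives a split for weight.
- Step 3 shows that restriction raises power only if the link is largely absent in controlled subjects.

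**Conclusion.** The concern holds as an omitted covariate, not as a wrong outcome or a wrong population. Each B.1.3 model leaves out the Screening value of its own outcome, against the plan's practice for Fugl-Meyer and PACES. The precision cost is a residual variance 18% to 43% higher for assumed rho of 0.7 to 0.4, and less for a very stable measure. The risk of a false association is real but conditional: none at c = 0, about 7% to 10% rejection at c = 0.2, and about 13% to 25% at c = 0.3, for rho of 0.7 to 0.5. The values of rho and c are assumptions and should be read as a range. Objective B.1.3 belongs to a secondary aim, and the primary non-inferiority conclusion does not depend on it.

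**What to change.** In 8.5, add the Screening value of the same measure (weight, systolic or diastolic pressure) as a covariate in each B.1.3 model, including the versions with the interaction term. Keep the all-subject analysis as the main one and keep alpha at 0.017. If the sponsor wants an analysis of subjects above a risk-factor target at Screening, fix the target in the SAP before unblinding, include the Screening covariate there too, and label the analysis supportive.

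The cost is a line of SAP text and one degree of freedom per model. The Screening values are in the data collection schedule (5.3), so no new measurement is needed for the covariate.

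One separate matter should be settled in the same edit. Section 8.5 places the second weight and blood pressure measurement at the Post-Therapy Visit. The schedule in 5.3 marks it at the 30 Day Follow Up, 5.3.4 lists neither measure, and 5.3.5 lists vital signs. These passages must be reconciled before the change can be computed as planned.

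### The three tests of knowledge gain against weight and blood pressure use single-step Bonferroni; Holm's step-down would be modestly more efficient at the same family-wise error (optional refinement)

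*Combined protocol and SAP*

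**What the plan says.** Section 1.2 (Specific Aim 2) sets the hypothesis labelled B.1.3: "Increased stroke knowledge will be positively correlated with improvement in weight and blood pressure control".

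Section 8.5, under Stroke education, turns this into three association analyses, with outcomes "change in weight, change in systolic blood pressure, and change in diastolic blood pressure". Each model is fitted "controlling for days from stroke onset to randomization, Stroke Knowledge Exam score at Screening Visit, age, and enrollment site", and each is judged "using a Bonferroni-adjusted alpha = 0.017". The section then adds: "again, analyses will be repeated by adding a time X group interaction term".

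Section 8 sets a two-tailed 0.05 level for all analyses. No step-down or gatekeeping procedure appears anywhere in the document. No effect size, correlation or power is given for these three tests; the target of 124 subjects with follow-up data was set for the Fugl-Meyer endpoint.

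**The concern.** With one fixed cut-off, each outcome must reach 0.017 whatever the other two show. Holm's procedure relaxes the threshold after each rejection and still protects the family at 0.05, with no assumption about how the tests are correlated. That matters here because systolic and diastolic pressure will move together.

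Take p-values of 0.010, 0.020 and 0.040. The plan as written declares one association. Holm declares all three: 0.010 is below 0.0167, then 0.020 is below 0.025, then 0.040 is below 0.05. At stake is some avoidable loss of power at the second and third ordered tests of a secondary hypothesis.

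**Working it through.** **The plan's figure.** Bonferroni for three tests at 0.05 is 0.05/3 = 0.01667, which is 0.017 at the printed precision. The figure reproduces.

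**Holm thresholds.** Smallest p against 0.05/3 = 0.0167; if rejected, the next against 0.05/2 = 0.025; if rejected, the largest against 0.05. Anything that Bonferroni at 0.05/3 rejects, Holm also rejects.

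**Family-wise error when no association is real.**
- Independent tests: 1 − (1 − 0.05/3)³ = 0.0492 for Bonferroni at 0.05/3, and the same for Holm. At the printed cut-off, 1 − (1 − 0.017)³ = 0.0501.
- Correlated tests (values below), by simulation: about 4.5% for Holm and 4.6% for 0.017.
- Some associations real and some not: Holm's simulated error stayed at or below 4.6%.

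**Power, by simulation of three two-sided z-tests.** From the documents: 124 subjects, the covariate list and the 0.017 cut-off. Assumed, because the documents are silent:
- All 124 subjects contribute to these analyses.
- The true partial correlation r lies between 0.10 and 0.30.
- The test statistics correlate 0.7 (systolic with diastolic) and 0.2 (weight with either pressure).
- Residual degrees of freedom are 124 − 14 = 110. With the eight sites assumed in section 12, the model would have an intercept, knowledge gain, three other covariates and seven site terms, which is 12 parameters and 112 degrees of freedom. The allowance of 14 is close to that and slightly cautious.

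Mean of each test statistic = r/√(1 − r²) × √110. For r = 0.25: 0.25/0.9682 × 10.488 = 2.71.

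All three associations real, plan at 0.017 against Holm:

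| r | Weight: plan → Holm | Each pressure: plan → Holm |
|---|---|---|
| 0.10 | 9% → 10% | 9% → 10% |
| 0.15 | 21% → 24% | 21% → 25% |
| 0.20 | 40% → 47% | 40% → 46% |
| 0.25 | 63% → 71% | 63% → 70% |
| 0.30 | 82% → 89% | 82% → 88% |

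Before rounding, the gain runs from about 1 point at r = 0.10 to about 8.5 points (weight, r = 0.25).

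Fewer associations real, r = 0.25:
- Both pressures only: about 62.6% → 65.4% for each, a gain of about 3 points.
- Weight only: 62.6% → 62.6%.
- Systolic only: 62.7% → 62.5%.

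Chance of at least one rejection, all three real: about 68% under either rule at r = 0.20 (0.3 points lower with Holm) and about 88% under either at r = 0.25.

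**The case against.** The strongest reply is that nothing here is wrong. Bonferroni is valid, prespecified and simple, and the family is one association hypothesis within a secondary aim. The larger gains need all three associations to be real and of moderate size; the documents support neither assumption. All of that stands, and it limits the point to an optional refinement.

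It is also true that Holm's dominance is over exactly 0.05/3. The printed 0.017 is a shade looser: a lone p of 0.0168 passes the plan and fails Holm. With only one real association this cancels the small gain, so the power given up by the present rule is not always recoverable.

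Two stronger readings are tempting, and the documents do not support them.

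- *All three outcomes must pass.* A reader might take B.1.3, which names weight and blood pressure together, as a joint requirement and headline the chance that all three pass (about 35% → 53% at r = 0.25). No such rule is stated. If it were, each outcome could be tested at the full 0.05 without adjustment (about 55% in the same setting), and neither Bonferroni nor Holm would be needed.
- *The cut-off breaches 0.05.* A reader might note that 3 × 0.017 = 0.051. That sum is an upper bound and the excess is rounding; the error is 5.0% under independence and about 4.6% under the assumed correlations.

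Two other matters in the same part of section 8.5 arguably deserve more attention. It does not say whether the repeated interaction analyses belong to the adjusted family. It also places the second weight and blood pressure measurement at the Post-Therapy Visit, while the section 5.3 schedule marks it at the 30 Day Follow Up. Those passages need reconciling whichever multiplicity rule is used.

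**Conclusion.** The point holds as a low-severity efficiency improvement, not as an error. Holm gives the same 5% family-wise guarantee under any dependence. The gain is about 1 to 9 points of per-outcome power if all three associations are real, about 3 points if only the two pressures are (r = 0.25), and nil if only one is. The chance of finding at least one association is essentially unaffected. These sizes rest on assumed partial correlations, test correlations and complete data on 124 subjects. That Holm never rejects fewer hypotheses than Bonferroni at 0.05/3 does not depend on those assumptions. The primary endpoint, the margin and the sample size are untouched.

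**What to change.** In section 8.5, replace "using a Bonferroni-adjusted alpha = 0.017" with: *with family-wise error for the three outcomes controlled at 0.05 by the Holm step-down procedure (smallest p against 0.05/3; if rejected, next against 0.05/2; if rejected, largest against 0.05)*.

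The cost is one clause and no new data. Simultaneous confidence intervals that match Holm are slightly less simple than Bonferroni intervals, but section 8.5 plans none for these tests. The change should be made before results are seen, because a later switch would look driven by the data. If the sponsor prefers the simplicity of single-step Bonferroni, keeping it is defensible.
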